**Study Protocol:**

**Subject Recruitment:** Subjects will be consented in the collaborating surgeons offices or in pre-admission testing. Every effort will be made to consent subjects prior to day of surgery. If a patient is referred or identified any time after those visits, they may be consented in the preoperative area.

**Anesthetic management per protocol:** For enrolled patients, anesthetic management will be left to the discretion of the attending anesthesiology provider. As per our usual clinical practice, Rocuronium or vecuronium will be used as the non-depolarizing NMB and that where sedation is desired and appropriate, The patients will be transferred to the CTICU intubated and on a propofol infusion and/or dexmedetomidine per our usual clinical practice.

Upon CTICU arrival, determination of continued eligibility will be determined. If the decision is made to continue on a fast-track extubation pathway, eligible patients will be randomized, investigational pharmacy will be contacted for study drug. 30 minutes after the ICU admission, propofol will be discontinued. Precedex may be continued per clinical discretion. The participant will be randomized to either receive Sugammadex or placebo. A qualitative train-of-four measurement will be obtained. The administration of the study and placebo compounds will be performed by CTICU nurses who will receive the drugs in a blinded fashion from the departmental research pharmacy. The level of neuromuscular blockade will be measured by accelerometer before and after the drug/placebo administration by the research coordinator. This will be done by placing a sheet over the limb being tested, so that the clinical team remains blinded to the results of the drug /placebo administration. The study drug will be supplied by Merck. Patients will be initiated on SIMV with 40% FiO2, tidal volumes 8-10 ml/kg and PEEP of 5.

Ten minutes after the drug administration, if the patient is able to lift head and remains hemodynamically stable, the patient will be switched to CPAP mode of ventilation for 30 minutes. At the end of the CPAP trial tidal volumes, Rapid Shallow Breathing Index (RSBI) and ABG will be assessed. The patient will be extubated if he/she is not hypoxic/ hypercarbic, has RSBI<100 and has TV >300 cc. The final clinical decision to extubate the patients will be taken by the CTICU team.

If a patient fails the 30 minute CPAP criteria, the ICU intensivist will be immediately notified. Every attempt will be made to correct the underlying cause of CPAP failure, and a prompt reassessment will be made as deemed appropriate by the intensivist to reattempt CPAP versus continuing controlled mechanical ventilation.

It is estimated conservatively that the study personnel will randomize 3 patients per week allowing for data collection to be completed within 1 year of study commencement. Data analysis and dissemination of findings will be conducted over the subsequent 6 months by the study institution investigators per the publication plan below.

Blinded analyses of the data will be performed by the study investigators along with the departmental statistician in the Department of Anesthesiology at the Yale School of Medicine.

**Variables/Time Points of Interest:** The primary outcome is the time to extubation, which will be the duration from arrival to the ICU to the extubation time. Participants' blood pressure, heart rate, and chest tube output will be tracked from arrival to the CTICU until extubation per ICU protocol.

**Statistical Methods:** Baseline comparability. We expect that the randomization process will produce reasonably comparable groups. However, the adequacy of the randomization will be assessed by comparing the distribution of baseline demographic and clinical characteristics among the intervention groups. Comparability for continuous variables will be examined graphically and by summary statistics (means, medians, quartiles, etc.). Categorical variables will be examined by calculating frequency distributions.

**Proposed statistical test/analysis:** Positively skewed variables will be log-transformed prior to hypothesis testing. For the primary outcome, a two-sided Student's t-test will be used to compare the time to extubation between the two groups. If necessary, covariate adjustment will be made using the multiple linear regression analysis method. Differences between means and 95% confidence intervals will be estimated to describe the magnitude of intervention difference between the two groups. As part of sensitivity analyses, the time-to-extubation outcome will be also analyzed by the Cox regression model. To compare the categorical adverse events between two groups, chi-square test or Fisher's exact test will be used.

**Missing Data:** Prevention is the most obvious and effective manner to control bias and loss of power from missing data. Therefore, several strategies (e.g., timely data entry and daily missing data report) will be imposed to limit the likelihood that missing data will occur during this study. This protocol will follow the intention to treat principle, requiring follow-up of all subjects randomized regardless of the actual treatment received.

**Power analysis:** Our 'in-house' historical data ( $n = 73$ ) showed that after excluding outliers greater than the 80th percentile, patients undergoing isolated CABG demonstrated a mean of 8.39 hours to extubation (SD 2.89). Although we anticipate a Hawthorne effect demonstrating reduced time to extubation in both the active and placebo arms of the present study, we have conservatively chosen to maintain power based on historical data. We therefore estimate that 45 subjects per group will give us 90% power to detect a clinically relevant effect size of 2-hours difference between active and placebo groups at an alpha value of 0.05 using a two-sided two-sample t-test. To allow for post consent, pre-randomization study drop out, we will aim to enroll a total of 110 ( $90 + 20 = 110$ ) subjects.

Per-protocol Sensitivity Analysis: In parallel with the primary analysis, if exclusions above occur post randomization but prior to drug administration, the investigators will conduct a parallel "per-protocol" sensitivity analysis.

Drug supplies will be supplied by the sponsor.

**Adverse Experience Reporting:** Throughout the duration of the study, researchers will adhere to good clinical practice and the guidelines of the institution. Patient vitals will be continuously monitored during and after the administration of the test drug. A data and safety monitoring board (DSMB) consisting of the head nurse and a senior critical care staff will meet monthly to discuss any serious events. Any incidence of anaphylaxis or unexplained hypotension requiring initiation of pressors or cardiac pacing within 5 minutes of drug administration will be reported and evaluated. Increases in chest tube output considered clinically significant by the critical care team will be noted. Any of these adverse events will trigger an analysis by the DSMB. If the DSMB determines that study drug may be causing an increase in adverse events, the study will be suspended until the DSMB is able to fully review the events and make a recommendation in consultation with the Yale Human Investigations Committee. The local Merck research

representative will also be notified about the events. If the data monitoring board and/or institutional review board (IRB) view that the study is unsafe, the study will be discontinued.

**Specific Safety Events to Be Reported During Manuscript Preparation:** For manuscript preparation, the rates of hypotension, anaphylaxis, and bleeding (i.e. Chest Tube output) will be reported and compared between active and placebo groups.

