4. Determination that the patient will require prolonged mechanical ventilation possibly requiring muscle relaxation based on the intraoperative course and clinical judgment of the study PI or collaborating intensivists.
5. Intraoperative hypoxia or on arrival to the ICU. (Please see Study Flowchart).
6. Cardiac arrest
7. Sudden arrhythmia (Ventricular tachycardia runs/sudden bradycardia with improper pacemaker detection/function) precluding fast-track extubation protocol.
8. Need for two or more inotrope initiation precluding fast-track protocol. Only a single vasopressor/inotrope may be initiated without excluding the subject.
9. Postoperative ST changes.

10. A positive standard of care pregnancy test during your pre-operative evaluation

9. How will **eligibility** be determined, and by whom?

Eligibility at pre-op and post-op will be based on protocol specific inclusion and exclusion criteria and will be determined by the PI or Sub-I's in collaboration with the ICU attending physician

10. **Risks:** Describe the reasonably foreseeable risks, including risks to subject privacy, discomforts, or inconveniences associated with subjects participating in the research.

Sugammadex is generally safe and well tolerated. Potential risks associated with sugammadex are: hypersensitivity, including anaphylaxis/anaphylactic shock – previous trials suggest this risk is small. Cardiac arrhythmias including bradycardia & tachycardia where intervention is rare and responsive to usual treatment. Other reported risks include nausea, vomiting, constipation.

Bleeding was originally thought to be a side effect, but studies have since showed that Sugammadex falsely elevates the PTT without increasing bleeding risk. (see reference on last page.)

11. **Minimizing Risks:** Describe the way the above-mentioned risks will be minimized.

Patients will all be in a critical care environment and monitored very closely including: blood pressure, heart rate, and chest tube output will be tracked from arrival to the CTICU until extubation per ICU protocol. Subtle changes in the patient's hemodynamic status are easily seen and treated if necessary.

12. **Data and Safety Monitoring Plan:** Include an appropriate Data and Safety Monitoring Plan (DSMP) based on the investigator's risk assessment stated below. (Note: the HIC will make the final determination of the risk to subjects.)

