- e.) Unrelated: Adverse event is clearly not related to investigational procedures(s)/agent(s).

4. Plan for Grading Adverse Events:

The following scale will be used in grading the severity of adverse events noted during the study:

1. Mild adverse event
2. Moderate adverse event
3. Severe

5. Plan for Determining Seriousness of Adverse Events:

Serious Adverse Events:

In addition to grading the adverse event, the PI will determine whether the adverse event meets the criteria for a Serious Adverse Event (SAE). An adverse event is considered serious if it results in any of the following outcomes:

1. Death;
2. A life-threatening experience in-patient hospitalization or prolongation of existing hospitalization;
3. A persistent or significant disability or incapacity;
4. A congenital anomaly or birth defect; OR

5. Any other adverse event that, based upon appropriate medical judgment, may jeopardize the subject's health and may require medical or surgical intervention to prevent one of the other outcomes listed in this definition.

An adverse event may be graded as severe but still not meet the criteria for a Serious Adverse Event. Similarly, an adverse event may be graded as moderate but still meet the criteria for an SAE. It is important for the PI to consider the grade of the event as well as its "seriousness" when determining whether reporting to the IRB is necessary.

Only the following adverse events will be tracked. These AE's will trigger an immediate DSMB review; any incidence of anaphylaxis; unexplained hypotension requiring initiation of pressors; cardiac pacing within 5 minutes of drug administration; tachycardia, bradycardia or onset of atrial fibrillation; or increases in chest tube output considered clinically significant by the critical care team. The DSMB will be notified within 2 business days of determination by telephone or email. A written report will be provided within 7 days of the determination. Any incidents meeting SAE criteria will be reported per the IRB reporting policy.

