**Protocol Amendments:**

Three changes were made to the protocol within the first year of initiation to generalize the inclusion criteria due to slow recruitment rates:

1. Originally the trial's inclusion criteria was patients undergoing isolated coronary artery bypass grafting. It was expanded to allow for coronary artery bypass grafting (CABG), aortic valve replacement (AVR) or coronary artery bypass grafting and aortic valve replacement (CABG and AVR).
2. The exclusion criteria for postoperative temperature was changed from 36.2° C to 35.5° C.
3. Low dose pressors infusion was allowed as long as it did not preclude fast track protocol as adjudicated by the clinical team that was blinded to the arm allocation.

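### The hypotension event counts pressor starts only, although patients may be randomised with a pressor already running; dose increases should count too (minor).

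*SAP*

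**What the plan says.** **Monitoring.** Under Variables/Time Points of Interest the SAP says: "Participants' blood pressure, heart rate, and chest tube output will be tracked from arrival to the CTICU until extubation per ICU protocol". The protocol puts the same tracking under Minimizing Risks (Section I, 11), with the comment that "Subtle changes in the patient's hemodynamic status are easily seen and treated if necessary".

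**The defined event.** The protocol's Data and Safety Monitoring Plan (Section I, 12, item 5) limits adverse event tracking to a stated list, and each listed event triggers immediate DSMB review. The blood pressure item is "unexplained hypotension requiring initiation of pressors". The heart rhythm item is "tachycardia, bradycardia or onset of atrial fibrillation". The SAP, under Adverse Experience Reporting, uses the same pressor-start condition for hypotension.

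**Who may be on a pressor at randomisation.** Protocol Section I, 8, post-recruitment exclusion 8: "Only a single vasopressor/inotrope may be initiated without excluding the subject". SAP, Protocol Amendments, item 3: "Low dose pressors infusion was allowed as long as it did not preclude fast track protocol".

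**What is compared by arm.** SAP, Proposed statistical test/analysis: "To compare the categorical adverse events between two groups, chi-square test or Fisher's exact test will be used". For the manuscript, the SAP says that "the rates of hypotension, anaphylaxis, and bleeding (i.e. Chest Tube output) will be reported and compared between active and placebo groups". That sentence gives no criterion for hypotension and has no heart rate item.

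**The concern.** The event definition does not fit everyone whom the eligibility rules admit. For a patient on no pressor, a treated fall in pressure normally means a start, and it is counted. For a patient already on an infusion, the natural first response is to raise it. That is not a start, and no other item on the closed list covers it.

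Two things are at stake. First, the DSMB would not be told of such a fall. Second, if the manuscript's hypotension rate follows the defined event, the by-arm comparison would miss it as well. The trial's title promises safety as well as efficacy, and the protocol's Background says that use of the drug after cardiac surgery is limited by a lack of supportive data. It also mentions scattered reports of hypotension. A count that misses part of the treated falls weakens the evidence on that question.

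A smaller gap sits beside it. The protocol's Risks section (Section I, 10) names bradycardia and tachycardia as risks of the drug, and they are on the tracked list, but they are not among the events that the SAP says the manuscript will compare.

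**Working it through.** **1. The plan's own figure.** Inputs from the Power analysis: difference 2 h, SD 2.89 h, two-sided alpha 0.05, 45 per group. The standardised difference is 2/2.89 = 0.692, and the noncentrality is 0.692 × √(45/2) = 3.28 on 88 degrees of freedom. Power is 90.1%, so the stated 90% reproduces. I use 45 per arm below.

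**2. Tracing one patient through the rules.**

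| Response to an unexplained post-dose fall | Counted as the defined event? |
|---|---|
| No pressor running, one started | Yes |
| One agent running, a second started | Yes, as a start |
| One agent running, its dose raised | No |

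Only the third row escapes. The documents do not say how many patients arrive on a pressor or how often falls are treated in this way.

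**3. Effect on the count (all rates assumed).** Let the true rates of treated falls be 20% (active) and 3% (placebo), and let h be the share handled by raising a running dose, equal in both arms. Counted rate = true rate × (1 − h). Power is exact: the binomial probabilities are summed over all pairs of counts with p ≤ 0.05. The test is chi-square without continuity correction when all expected counts are at least 5, and Fisher's exact test otherwise.

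| h | Counted rates | Difference (points) | Expected events, 45 v 45 | Power |
|---|---|---|---|---|
| 0 | 20% v 3% | 17.0 | 9.0 v 1.35 | 70.3% |
| 25% | 15% v 2.25% | 12.75 | 6.75 v 1.01 | 45.7% |
| 50% | 10% v 1.5% | 8.5 | 4.5 v 0.68 | 18.3% |

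With h equal in the two arms the ratio of rates stays at 6.7 (20/3), so the loss is in the absolute difference and in power. Of 9.0 + 1.35 = 10.35 expected treated falls, 0.25 × 10.35 = 2.6 or 0.50 × 10.35 = 5.2 would not reach the DSMB.

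**4. A second way to model it.** Suppose instead that a share s of patients is already on a pressor and can have no counted start. This is a worst case, since a second agent would count. With assumed rates of 20% v 5%, counted rate = true rate × (1 − s):

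| s | Counted rates | Fisher power |
|---|---|---|
| 0 | 20% v 5% | 48% |
| 20% | 16% v 4% | 34% |
| 40% | 12% v 3% | 20% |
| 60% | 8% v 2% | 7% |

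The two models differ in size but agree in direction.

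**5. Would comparing the measured values be the better remedy?** At 45 per arm, a uniform shift of 0.5 SD (assumed) has 65% power as a comparison of means. As an event count it has 17%, 34% or 43% at placebo rates of 5%, 10% or 20%. Now suppose instead that 15% of active patients react with a 3 SD fall. Events then have 36% to 45% power (placebo rates 1% to 5%), and values have 38%, or 43% adjusted for the pre-dose value (correlation 0.5). If 20% react, events have 62% to 69% and values 57%, or 64% adjusted. If treatment limits the recorded fall to 1 SD, adjusted power is only 12% (15% reacting) to 18% (20% reacting). The gain is clear only under a uniform shift, which the documents do not suggest.

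**The case against.** The plan does contain a by-arm safety comparison, and its manuscript sentence speaks of hypotension without any pressor condition. The pressor-start wording governs what is reported to the DSMB. The authors may intend the manuscript rate more broadly, so the by-arm loss is conditional. This stands. It does not rescue the DSMB trigger, where the start condition is explicit, and the closed list of tracked events makes the narrow reading of the manuscript rate the more natural one. If a broader meaning is intended, it is not written down.

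The assumed 20% v 3% is also far from scattered reports. That is fair: the figures show how the mechanism works and do not forecast its size. Bradycardia and tachycardia already fall under the general chi-square or Fisher comparison, so their absence from the manuscript list is a matter of wording.

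A reader might infer something stronger: that tracking blood pressure and heart rate without comparing the values by arm is itself a defect. The documents do not support that. The protocol presents the tracking as bedside monitoring and names only extubation time as its outcome of interest. Bleeding is equated with chest tube output, a measured quantity with no cut-off, so it is not even certain that everything compared is categorical. A comparison of values gains little for the isolated reactions that the Background describes. Tracking follows an ICU protocol not seen here, so a short post-dose window might hold one charted value or none.

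**Conclusion.** The point holds as a gap in an event definition, and it is minor. On the visible text, an unexplained post-dose fall treated by raising a running pressor is not an event. It would not trigger DSMB review, and it would be missing from the by-arm hypotension rate unless that rate is meant more broadly than the defined event.

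The definitional gap needs no assumed figure; its size does. At 45 per arm, with 20% v 3% assumed and 25% or 50% of falls handled by dose increase, the counted difference falls from 17 to 12.8 or 8.5 points and power from 70% to 46% or 18%. If few patients arrive on a pressor, the loss is small.

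The primary analysis and sample size are untouched. The study flowchart, the DSMB charter, the ICU protocol and part of the SAP are not in the text reviewed. A definition given there could close the gap.

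**What to change.** 1. In the protocol's Data and Safety Monitoring Plan and in the SAP's Adverse Experience Reporting, define the event as unexplained hypotension that requires a pressor to be started or the dose of a running pressor to be raised.
2. State that the manuscript's hypotension rate uses this definition.
3. Show pressor starts, pressor dose increases and pacing after injection by arm, in one small table.
4. Add bradycardia and tachycardia to the events that the manuscript will compare.

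Optional, where charting allows: a descriptive by-arm summary of the lowest mean arterial pressure and the lowest and highest heart rate in the 10 minutes after injection, which ends before the head-lift check and the switch to CPAP. Give differences adjusted for the last pre-dose value, with 95% confidence intervals and no significance claim. Use one charting interval for both arms and show pressor changes beside the values, because treatment can hide a fall.

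Cost: a few lines of wording, a little extra data entry from the medical record, a somewhat higher event count and more DSMB notifications. Patients undergo no new procedure and no more of them are needed.

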2. Patients will be transferred to the CTICU intubated and on a propofol infusion and/or dexmedetomidine (Precedex) from the operating room. Both meds are used SOC.
3. Upon CTICU arrival, the patients surgeon and CTICU intensivist will determine if patient is able to proceed with fast-track extubation. Determination of continued eligibility based on the post-recruitment pre-randomization exclusion criteria will be determined by a member of the study team. Eligible patients will be randomized, investigational pharmacy will be contacted for study drug and within 30 minutes of the ICU admission, propofol will be discontinued. Precedex may be continued per clinical discretion.
4. The participant will be randomized to receive Sugammadex or placebo. The enrolled patients will be assigned to the study and control arms in a 1:1 ratio.
5. IDS will provide the Sugammadex (2mg/kg) vs. Placebo in a syringe. A qualitative train-of-four measurement will be obtained. The administration of the study drug and placebo compounds will be performed by CTICU nurses who will receive the drugs in a blinded fashion from the departmental research pharmacy. The study drug will be supplied by Merck.
6. The clinical care provider has the discretion to determine the appropriate ventilation settings on a case-by-case basis, in accordance with the suggestion that patients will be initiated on SIMV rate of 14 with 60% FiO₂, tidal volumes 8-10 ml/kg and PEEP of 7.
7. Ten minutes after the drug administration, if the patient can lift their head and remains hemodynamically stable, the patient will be switched to CPAP mode of ventilation for 30 minutes. At the end of the CPAP trial tidal volumes, Rapid Shallow Breathing Index (RSBI) and ABG will be assessed. The patient will be extubated if he/she is not hypoxic/ hypercarbic, has RSBI<100 and has TV >300 cc.
8. If a patient fails the 30-minute CPAP criteria, the ICU intensivist will be immediately notified. Every attempt will be made to correct the underlying cause of CPAP failure, and a prompt reassessment will be made as deemed appropriate by the intensivist to reattempt CPAP versus continuing controlled mechanical ventilation.

Study participation will end when the patient is successfully extubated. AE assessment will be performed in the period immediately following extubation.

5. Genetic Testing N/A

6. **Subject Population:** Provide a detailed description of the types of human subjects who will be recruited into this study.

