These UPIRSOs/SAEs will be reported to the IRB in accordance with IRB Policy 710, using the appropriate forms found on the website. All related events involving risk but not meeting the *prompt* reporting requirements described in IRB Policy 710 should be reported to the IRB in summary form at the time of continuing review. If appropriate, such summary may be a simple brief statement that events have occurred at the expected frequency and level of severity as previously documented. In lieu of a summary of external events, a current DSMB report can be submitted for research studies that are subject to oversight by a DSMB (or other monitoring entity that is monitoring the study on behalf of an industry sponsor).

7. Plan for reporting adverse events to co-investigators on the study, as appropriate the protocol's research monitor(s), e.g., industrial sponsor, Yale Cancer Center Data and Safety Monitoring Committee (DSMC), Protocol Review Committee (PRC), DSMBs, study sponsors, funding and regulatory agencies, and regulatory and decision-making bodies.

For the current study, the following individuals, funding, and/or regulatory agencies will be notified (choose those that apply):

- All Co-Investigators listed on the protocol.
- Study Grantor (Merck)
- Other Data Safety Monitoring Board (DSMB)
- Yale University IRB

The principal investigator [name] will conduct a review of all adverse events upon completion of every study subject. The principal investigator will evaluate the frequency and severity of the adverse events and determine if modifications to the protocol or consent form are required.

See also DSMB charter attached.

13. Statistical Considerations: Describe the statistical analyses that support the study design.

Variables/Time Points of Interest

The primary outcome is the time to extubation, which will be the duration from arrival to the ICU to the extubation time.

Proposed statistical test/analysis: Positively skewed variables will be log-transformed prior to hypothesis testing. For the primary outcome, a two-sided Student's t-test will be used to compare

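### Does covariate adjustment with no stated trigger leave the primary analysis of time to extubation undecided?

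*SAP*

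**What the plan says.** The Protocol (Section I, item 13, Statistical Considerations) and the SAP (Proposed statistical test/analysis) carry the same text. The primary outcome is the time from ICU arrival to extubation, and the test named for it is a two-sided Student's t-test. Two qualifiers stand beside that sentence. One concerns scale: "Positively skewed variables will be log-transformed prior to hypothesis testing". The other concerns covariates: "If necessary, covariate adjustment will be made using the multiple linear regression analysis method".

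Three other statements bear on the point:

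- The Cox model has an explicit status: "As part of sensitivity analyses, the time-to-extubation outcome will be also analyzed by the Cox regression model". The SAP's per-protocol analysis is also labelled a sensitivity analysis. The regression has no label.
- Under Baseline comparability the SAP says that "the adequacy of the randomization will be assessed by comparing the distribution of baseline demographic and clinical characteristics among the intervention groups". It will do so with graphs, summary statistics and frequencies. It gives no threshold and no link to the adjustment sentence.
- On who analyses the data, the SAP says: "Blinded analyses of the data will be performed by the study investigators along with the departmental statistician".

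The Power analysis paragraph in both documents rests on the unadjusted two-sample t-test: 45 per group, 90% power, a 2-hour difference, SD 2.89 hours, two-sided alpha 0.05.

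**The concern.** An adjustment with no trigger, covariate list or status can in principle be decided after the data are seen. If the adjusted and unadjusted results differ, the plan does not state outright which one is the trial's answer. Choosing between them by p-value would raise the false-positive rate above 5%.

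Plausible covariates exist. Procedure type is one: there are now three eligible procedures, and the SAP's Protocol Amendments section records that eligibility was widened from isolated CABG. The depth of neuromuscular block is another. Neither is named in any analysis. A single adjusted model fixed in advance appears to remove the ambiguity for almost nothing, and it might gain power.

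**Working it through.** **Inputs from the documents.** n = 45 per arm, difference 2 h, SD 2.89 h, two-sided alpha 0.05, 1:1 allocation. **Assumed.** The share of outcome variance that covariates explain (R²), because the documents give none. The figures are in hours because no log-scale SD is given.

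**1. The plan's own figure.** Noncentrality = 2 / (2.89 × √(2/45)) = 2 / 0.6093 = 3.283. With 88 degrees of freedom the critical value is 1.987 and power is 0.901. Solving for 90% power gives 44.86 per arm, so 45. The sample size matches the t-test that the plan names.

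**2. Type I error under different readings of the adjustment sentence.** Results are from 20,000 simulated null trials per R², so the Monte Carlo standard error near 5% is √(0.05 × 0.95 / 20,000) = 0.15 points. The covariates are block depth and procedure, with an assumed 60/25/15% procedure mix and R² split 4.5:1 between block and procedure.

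| Rule | R² 0.06 | 0.10 | 0.20 | 0.30 |
|---|---|---|---|---|
| Always the adjusted model | 5.0% | 5.1% | 5.0% | 4.9% |
| Adjust if imbalance p < 0.05 (about 10% of trials) | 4.9% | 4.7% | 4.3% | 4.2% |
| Adjust if standardised difference > 0.25 (about 59% of trials) | 4.9% | 4.8% | 4.4% | 4.0% |
| Report the smaller p-value | 6.2% | 6.7% | 7.0% | 7.5% |

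The middle rows behave as theory predicts. Given the covariates, the adjusted test has its nominal level. The unadjusted test rejects too often when a prognostic covariate is imbalanced and too rarely when it is balanced. Adjusting only in the imbalanced trials removes the excess and keeps the deficit, so the overall rate falls slightly. How often adjustment is triggered varies greatly with the threshold, but the error rate hardly moves. Only selection by result takes it above 5%.

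**3. What a fixed adjusted primary model would cost or gain.** With k covariate terms:

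noncentrality = 2 / [2.89 × √(1 − R²) × √((2/45) × (1 + k/(87 − k)))], on 88 − k degrees of freedom.

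For k = 3 and R² = 0 the inflation factor is 1 + 3/84 = 1.036, the noncentrality is 3.226 and power is 0.891.

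| Terms | R² 0 | 0.10 | 0.20 | 0.30 |
|---|---|---|---|---|
| 3 (procedure, linear block) | 0.891 | 0.920 | 0.946 | 0.968 |
| 6 (procedure, block as five categories) | 0.879 | 0.910 | 0.938 | 0.963 |

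The model breaks even with the t-test at R² = 0.035 (three terms) or 0.070 (six terms). If any block reading is missing, a missing-reading indicator makes these four and seven terms, with power at R² = 0 of 0.887 and 0.875. Those are losses of 1.4 and 2.6 points from 0.901.

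The large gains need block to predict extubation time in both arms, which is doubtful for a drug that reverses block. Suppose it predicts only on placebo, with correlation 0.5. In units of the outcome variance the common slope is 0.25, and the mean residual variance is (0.8125 + 1.0625)/2 = 0.9375, so R² = 0.0625. Power is then 0.909 with three terms, 0.899 with six and 0.895 with seven: a gain of under one point, or a small loss.

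**4. Whether block is usable as a baseline covariate.** Both documents say: "A qualitative train-of-four measurement will be obtained". In both, that sentence comes after the randomisation step, and neither says that the reading precedes the dose. The accelerometer reading is described as before and after the dose, but only in the SAP. The SAP also allows for exclusions between randomisation and dosing, and such patients may have no reading although intention to treat keeps them. Procedure type is the only candidate certain to be known for every patient.

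**The case for a change.** The strongest case for a change is that the regression is the one additional analysis of the primary outcome without a label, and that the baseline-comparability paragraph supplies no rule. Analysis with masked arm labels is not a full safeguard, because an analyst can still see both p-values. Nor does the plan say that the model is fixed before unblinding. The smaller-p figure is not the extreme either. In a separate simulation (10,000 null trials per setting), picking the best subset of three covariates gave 7.9% to 10.7% for R² from 0.10 to 0.30. The minimal remedy, a line calling the t-test primary and the regression a sensitivity analysis, would cost no power and no data.

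The description of the gap stands, and so does the arithmetic. The inference to a needed change does not. The inflated figures describe an analyst who chooses by result, which nothing in either document invites. The minimal remedy would write down what the paragraph already conveys: a specific test is assigned to the primary outcome and the sample size is computed for that test. The larger remedy, an adjusted model as the single primary result, would displace a valid and powered test after recruitment had begun, as the SAP's Protocol Amendments section shows. It would also need rules for missing readings and sparse procedure categories, in exchange for a gain that the documents cannot support.

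**Conclusion.** The concern does not call for a change. The primary analysis is identified and valid, and it agrees with the stated sample size (power 0.901 at 45 per arm). Leaving covariates out of a randomised comparison is not an error. The missing trigger, covariate list and label are details that a statistician would fill sensibly, by reporting the t-test as the primary result and any adjusted estimate as support.

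On the imbalance reading, type I error stays between 4.0% and 4.9%. The 6.2% to 7.5% range belongs to selective reporting and not to the plan as written. A fixed adjusted model would shift power from 0.901 to between 0.875 and 0.968, depending on an R² that the documents do not give, and the placebo-only scenario puts it between 0.895 and 0.909.

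These results assume the simulated procedure mix and covariate split, and an analysis in hours. The power levels also inherit an SD taken from isolated CABG patients with times above the 80th percentile excluded, so the comparisons between models are firmer than the absolute values. The conclusion would change only if the choice between the two estimates were made on their results.
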